5.3. Key Secondary Endpoint

5.3.1. Definition

The key secondary endpoint is the proportion of participants having HBsAg seroclearance 24 weeks after stopping all study interventions at Week 48. This endpoint will be called as “functional cure” at week 72 interchangeably in the rest of this document.

A participant will be defined as having achieved functional cure (FC) at Week 72 if he/she has:

- met the criteria for stopping NA treatment at Week 48, and
- had HBsAg seroclearance at Week 72 (i.e. 24 weeks after stopping all study interventions), and
- not required NA re-treatment between Weeks 48 and 72.

Seroclearance of HBsAg is defined as HBsAg level<LLOQ. It can be noted that a participant may achieve HBsAg seroclearance prior to Week 72, but the HBsAg level<LLOQ has to be shown at Week 72 to be counted as responder.

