Therefore, within the MCP-Mod framework, the MCP analysis to test the null hypothesis that none of the 3 JNJ-3989 doses (40 mg, 100 mg, and 200 mg)+NA is better than historical control NA (i.e. the flat dose response curve) will assume:

- the point estimate for the response rate of the “JNJ-3989 dose=0 mg historical NA” is 0.05,
- the estimated variance, on the logit scale, of the point estimate for the response rate of the “JNJ-3989 dose=0 mg historical NA” historical group is 0.0275.

Characterization of the dose-response model: The model averaging techniques (Bornkamp B. et al., 2009) across the candidate models will be utilized to derive the dose-response shape and to evaluate the desired dose(s) of JNJ-3989 (modeling step). The estimated dose response curve and the corresponding confidence band will be plotted against the JNJ-3989 dose range of 0 mg to 200 mg.

5.3.2.1.1.2. Scientific Question Part b: Pairwise Comparisons vs Historical Control

For the pairwise comparison against the fixed historical control value of 5% for Arms 1 and Arm 5, respectively, the Clopper-Pearson test will be used at one-sided 0.05 alpha level, based on a fixed sequence testing approach as described in Section 5.1.1.

5.3.2.1.1.3. Scientific Question Part c: Comparisons Among Combination Regimens

For the regimen-finding objective, the testing among the regimens (Arm 1, 3, and 5) will be performed at a one-sided 0.025 alpha level using the min test approach to provide evidence of superior efficacy of the triple regimen Arm 1 over the dual regimens Arm 3 and Arm 5, for

regulatory consideration. This analysis is performed at a more stringent α -level because it aims to support the selection of the combination drug therapy to be studied in confirmatory studies. The JNJ-3989+JNJ-6379+NA combination regimen Arm 1 will be declared statistically superior to the dual regimens Arm 3 and Arm 5, if both tests of Arm 1 vs Arm 3 and Arm 1 vs Arm 5 demonstrate statistical significance at the one-sided 0.025 level. The Mantel-Haenszel test for the difference of 2 proportions adjusted for the 2 randomization stratification factors will be applied.

Further, the functional cure efficacy endpoint will be summarized for the control Arm 6 with the point estimate paired with its 90% CI using the Clopper-Pearson exact method to assess the consistency with the assumed historical control value of 5%.

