For the MCP-step, the max trend test will be obtained for each of the imputed datasets and the multiplicity adjusted p-value associated with the largest T-test statistic will be saved. All p-values will be transformed to a Z-test statistic using the inverse cumulative distribution function of the standard normal distribution. The resulting 200 Z-test statistics and their standard error of 1 will be combined into an overall Z test result, using SAS PROC MIANALYZE.

For Mod-step, model averaging techniques across all 5 candidate models will apply to each imputed dataset and produce the weighted estimates across all models of the treatment effect across the JNJ-3989 dose range (0 mg and 200 mg). The standard errors will be obtained using bootstrapping techniques and then combined into one result using PROC MIANALYZE. The final response estimates on the logit scale for each dose level in the range 0 mg to 200 mg and their 90% CI will be back transformed to the original scale of proportion of responders and plotted with the corresponding 90% confidence band.

For pairwise comparisons against the fixed historical control value of 5% for Arm 1 and Arm 5, the estimated proportion with the asymptotic standard error will be obtained for each dataset. Then the results from these multiple imputed datasets are combined (pooled) for obtaining the overall inference and p-value in a way that accounts for the variability between imputations ([Ratitch B. et al., 2013](#)). Depending on the amount of missing data, the number of imputed datasets to be generated will be increased appropriately to ensure robustness in the results ([Graham JW. et al., 2007](#)).

For comparisons amongst combination regimens (Arms 1, 3, and 5), the MH test will be performed for each dataset to generate individual estimates of the difference in proportions and the standard error adjusted on stratification factors. Then the results from these multiple imputed datasets are combined (pooled) for obtaining the overall inference and p-value in a way that accounts for the variability between imputations ([Ratitch B. et al., 2013](#)). Depending on the amount of missing data, the number of imputed datasets to be generated will be increased appropriately from the planned 200 to ensure robustness in the MI results.

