5.3.2.2. Sensitivity Estimators of the Main Estimand of the Key Secondary Endpoint

Sensitivity analyses will be conducted by constructing three sensitivity estimators for the key secondary primary estimand as defined in Section [5.3.2](#). One estimator will test the assumption of homogeneous treatment effect across the 2 randomization stratification factors, and the 2 other ones will use different missing data imputation rules.

5.3.2.2.1. Sensitivity Estimator 1 For the Main Estimand (LOCF) of the Key Secondary Endpoint

For this sensitivity estimator 2, the same statistical model (Clopper-Pearson and stratum-adjusted MH test), data included and approach to control the Type I error rate will be used as for the main estimator (Section 5.3.2.1). The assumption for missing data and the rule to handle missing data have changed.

5.3.2.2.1.1. Assumptions

- Missing Data for HBsAg are Missing Completely at Random ([Barnes A. et al., 2008](#))
- The treatment effect is homogeneous across strata

5.3.2.2.1.2. Missing Data Handling Rule

For sensitivity estimator 2, participants who withdraw from the study prior to Week 72 will be considered as non-responders. After taking into account all the intercurrent events and applying the intercurrent event strategies specified in Section 5.3.2, if a subject who did not experience any ICEs has missing response status for the key secondary efficacy endpoint then the LOCF approach will be used as follows.

If the HBsAg value is missing at Week 72, the Last Observation Carried Forward (LOCF) in conjunction with the next available observation imputation approach will be used. The non-missing value closest to Week 72 will be selected among the non-missing values which are no earlier than 12 weeks prior or no later than 12 weeks after Week 72. If 2 non-missing laboratory values are equidistant, the later observation will be preferred.

For Mod-step, model averaging techniques across the statistically significant candidate models obtained from the MCP step will be used to derive the dose-response shape (Mod step).

5.3.2.2.2. Sensitivity Estimator 2 For the Main Estimand (Tipping Point) of the Key Secondary Endpoint

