For this sensitivity estimator 3, the same statistical model (MCP-Mod, Clopper-Pearson and stratum-adjusted MH test), data included and approach to control the Type I error rate will be used as for the main estimator (Section 5.3.2.1). The assumption for missing data and the rule to handle missing data have changed.

5.3.2.2.2.1. Assumptions

- Missing Data for HBsAg are Missing Not at Random (MNAR)
- The treatment effect is homogeneous across strata

5.3.2.2.2.2. Missing Data Handling Rule

For sensitivity estimator 3, the tipping point approach with the exhaustive scenario's analysis will be applied.

Instead of imputing non-response for missing data, the following method will be utilized to vary the imputation of response for missing data. For participants with missing response data at Week

72, responder status will be imputed in an increasing manner by participant count for each treatment group. Specifically, for each participant with missing data at Week 72, a responder/non-responder status will be imputed starting with the scenario where all participants are non-responders up to the scenario where all participants are responders. This would include all possible scenario combinations of responder/non-responder status for all missing data, including scenarios where participants on any active Arm have worse outcomes than participants on placebo+placebo+NA. Within the exhaustive scenarios list, the ‘worst case scenario’ will be one of the cases where all participants with missing Week 72 data in the active regimen arms will be imputed to ‘non-responders’ and all participants with missing data at Week 72 in the placebo+placebo+NA arm will be imputed to “responders”. For each scenario, the same statistical model (MCP-Mod, Clopper-Pearson, and stratum-adjusted MH test), will be used as for the main estimator of comparisons vs historical control and comparisons amongst the combination regimens (Section 5.3.2.1.1) will be performed. A graphical display of the pvalue significance will summarize the results across all scenarios for this sensitivity estimator 3.

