5.3.2.3.1. Supplementary Estimator 1 (ITT Analysis Set + MI)

For this supplementary estimator, the same estimand defined in Section 5.3.2, statistical model (MCP-Mod, and stratum-adjusted MH test), assumptions and approach to control the Type I error rate, and the same MI rule to handle missing data will be used as for the main estimator (Section 5.3.2.1).

5.3.2.3.1.1. Data Included

All available data from ITT analysis set, after taking into account all the intercurrent events and applying the intercurrent event strategies specified in Section 5.3.2, will be included.

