5.3.4.1. Main Estimator

To assess the functional cure rate against the observed proportion in the control Arm 6, for this estimator, the same statistical model (MCP-Mod, and stratum-adjusted MH test), data included, assumptions, and MI approach for handling missing data and approach to control the Type I error rate will be used as for the main estimator of the main estimand for the primary endpoint (Section [5.2.2.1](#)). The MCP-Mod approach and pairwise statistical tests to compare with control will be based on the data from Arm 6 instead of historical control fixed value of 5%. The MCP-step will use the actual data from Arm 6, and statistical test to compare Arm 1 and Arm 5 to control will be the MH test as it compares 2-sample proportions.

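### Functional cure against 5%: the SAP names Clopper-Pearson for Arms 1 and 5, but its main multiple-imputation p-value comes from a pooled asymptotic test while the sensitivity analyses stay exact

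*SAP*

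**What the plan says.** Functional cure at Week 72 is the key secondary endpoint. In place of the study control arm it uses a fixed historical rate of 5%. For Arms 1 and 5 against that value, SAP 5.3.2.1.1.2 states that "the Clopper-Pearson test will be used at one-sided 0.05 alpha level, based on a fixed sequence testing approach". Under SAP 5.1.1, Arm 5 is tested only if Arm 1 succeeds.

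SAP 5.3.2.1.4 sets the missing-data rule for the same main estimator. It generates 200 imputed datasets. For these two comparisons "the estimated proportion with the asymptotic standard error will be obtained for each dataset", and the results are pooled to give the overall inference and p-value. It gives no formula for the standard error and does not mention Clopper-Pearson.

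The LOCF analysis (SAP 5.3.2.2.1), with the main estimator as its point of reference, says "the same statistical model (Clopper-Pearson and stratum-adjusted MH test), data included and approach to control the Type I error rate will be used". The tipping-point analysis (SAP 5.3.2.2.2) likewise keeps "the same statistical model (MCP-Mod, Clopper-Pearson and stratum-adjusted MH test), data included and approach to control the Type I error rate". LOCF describes its departure from the main estimator this way: "The assumption for missing data and the rule to handle missing data have changed". The tipping-point section says the same.

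**The concern.** A sensitivity analysis for missing data is informative when it holds the test fixed and varies the missing-data assumption. Here two things change at once: the missing-data rule, and the test (from a pooled asymptotic statistic to an exact binomial test). The SAP tells the reader that only the first has changed.

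The other parts of SAP 5.3.2.1.4 do not do this. The MCP step keeps its trend test within each imputed dataset and pools the resulting p-values on the Z scale. The comparisons among Arms 1, 3 and 5 keep the Mantel-Haenszel test. Only the comparison with 5% swaps its named test for another.

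Two things are at stake. Near the threshold the choice of test decides significance for Arm 1, and therefore whether Arm 5 is tested. A gap between the main and sensitivity results could also be misread as fragility to missing data. Dose finding by MCP-Mod and the triple-versus-dual comparison do not use this step.

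**Working it through.** The documents give no power or critical count for these comparisons, so there is no published figure to reproduce.

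**Inputs.** Null rate 0.05, one-sided level 0.05 and 200 imputations (SAP 5.3.2.1). Planned n is 90 for Arm 1 and 45 for Arm 5, with enrolment extended by about 5% (SAP 1.4). Spread evenly (my assumption), that is about 95 and 47.

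**Who can be affected.** Under SAP 5.3.1 a responder must have "met the criteria for stopping NA treatment at Week 48", must not have needed re-treatment, and must show seroclearance at Week 72. Under SAP 5.3.2.1.4 withdrawals before Week 72 count as non-responders. Imputation can therefore change status only for someone who stopped NA at Week 48, was not re-treated, is still in the study without a disqualifying event, and lacks a Week 72 value.

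**Step 1: nothing imputed (limiting case).** Exact p = P(X ≥ x | n, 0.05). Wald z = (p̂ − 0.05)/√(p̂(1 − p̂)/n).

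| Count | Exact p | Wald p |
|---|---|---|
| 8/90 | 0.0813 | 0.0974 |
| 9/90 | 0.0362 | 0.0569 |
| 10/90 | 0.0145 | 0.0325 |
| 5/45 | 0.0729 | 0.0960 |
| 6/45 | 0.0239 | 0.05004 |
| 7/45 | 0.0066 | 0.0254 |

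For 9/90, z = 0.05/√(0.1 × 0.9/90) = 1.581, so p = 0.0569. The exact test rejects from 9/90 and 6/45 (sizes 0.0362 and 0.0239). Wald rejects from 10/90 and 7/45 (sizes 0.0145 and 0.0066). At 6/45 the Wald result misses by a hair.

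**Step 2: one imputed value.** Assume 9 observed responders among 90 and one missing value imputed as a response with probability q = 0.1.

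- Wald, Rubin pooling: pooled proportion 9.1/90 = 0.10111. Mean within-imputation variance 0.0010097. Between-imputation variance 0.1 × 0.9/90² = 0.0000111. Total T = 0.0010097 + (1 + 1/200) × 0.0000111 = 0.0010209. z = 0.05111/√0.0010209 = 1.600, p = 0.0548.
- Exact-Z (exact p-values pooled on the Z scale): Z is 1.797 at 9/90 and 2.183 at 10/90. Mean Z = 0.9 × 1.797 + 0.1 × 2.183 = 1.836. Variance 1 + (1 + 1/200) × 0.09 × (2.183 − 1.797)² = 1.0135. Pooled p = 0.0341.
- Exact test in the tipping-point scenarios for this arm: 0.0362 if the missing value is a non-response and 0.0145 if it is a response.

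So in this example the main analysis fails at 0.0548 while both tipping-point scenarios succeed. No assumption about the missing value explains that; the test does.

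**Step 3: other cases, one imputed value.**

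| Case | Wald p | Exact-Z p |
|---|---|---|
| 9/95, q = 0.1 | 0.0657 | 0.0457 |
| 6/47, q = 0.1 | 0.0532 | 0.0271 |
| 6/45, q = 0.1 | 0.0482 | 0.0224 |
| 9/90, q = 0.5 | 0.0454 | 0.0254 |

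The decision differs in the first two rows and not in the last two.

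**Step 4: how far the gap reaches.** With nothing imputed, the critical counts coincide for n = 82 to 86, 96 to 100 and 41 to 44. At n = 90 the rules disagree only at a count of 9, which has probability 13.9% at a true rate of 10%, 5.2% at 15% and 0.5% at 20%. Power at a true 15% is 0.937 (exact) against 0.885 (Wald) for Arm 1, and 0.686 against 0.522 for Arm 5.

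**The case against.** The strongest reply is that the sections are compatible. The pooled step sits under the missing-data rule, which the sensitivity analyses say they change, and the tipping-point section points back to the analysis-methods section that names Clopper-Pearson. On that view, Clopper-Pearson applies to any single completed dataset, and an estimate with its standard error applies when 200 must be pooled. This reading is reasonable, and it answers anyone who infers that the main test has no definition at all. It does not remove the problem. The main p-value still comes from a different and, at these counts, weaker test than the named one, and the sensitivity analyses still differ from it in the test.

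Three further inferences are tempting, and the documents do not support them.

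- **Inflated Type I error.** A standard error taken at the 5% null would reject from 8/90 and 5/45, with sizes 0.081 and 0.073. But the SAP speaks of the estimated proportion with its standard error, which points to the observed rate. On that reading the test is conservative.
- **No test, or the wrong test, in the supplementary analyses.** SAP 5.3.2.3.1 lists "statistical model (MCP-Mod, and stratum-adjusted MH test), assumptions and approach to control the Type I error rate, and the same MI rule" and names no one-sample test, and SAP 5.3.4.1 says, for the analysis against Arm 6, that the "statistical test to compare Arm 1 and Arm 5 to control will be the MH test as it compares 2-sample proportions". The bracketed lists are shorthand, however: the LOCF list omits MCP-Mod although that section uses it. The one-sample test is inherited by reference, so the omission is editorial.
- **A disagreement rate for this trial.** Simulations with one to three missing values per arm gave disagreements from 0.6% to 14.0% in the main scenarios. No document gives the number of missing Week 72 values, and the simulated imputation is not the SAP's longitudinal HBsAg model. These rates are illustrations only.

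One caution about the remedy stands. In those simulations Wald never rejected when exact-Z did not, so restoring the exact test after unblinding can only help significance. That is a reason to date the change and show both results.

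**Conclusion.** The point holds in a limited form and should be fixed. For Arms 1 and 5 against 5%, the main multiple-imputation analysis departs from the test that the SAP names and that its sensitivity analyses use. Main and sensitivity results can therefore disagree for a reason unrelated to missing data.

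The size is modest. At the planned n with nothing imputed, it is one count per arm: 9/90, and 6/45 by a margin of 0.00004. The direction is a loss of power, not a false claim. The gap disappears at some arm sizes, and the analysed mITT count is not known in advance.

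This rests on reading the asymptotic standard error as the Wald form and on a normal reference for the pooled statistic. The imputed examples also rest on assumed responder probabilities.

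**What to change.** Use one test for Arms 1 and 5 against 5% in the main and sensitivity analyses.

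- **Preferred.** Keep the test named in SAP 5.3.2.1.1.2. In SAP 5.3.2.1.4, compute the one-sided Clopper-Pearson p-value in each imputed dataset, convert it to Z and pool with a standard error of 1, as that section already does for the MCP step. State a cap for p = 1 (for example 0.9999), because a dataset with no responders otherwise has no finite Z.
- **Alternative.** State that the pooled asymptotic test replaces Clopper-Pearson under multiple imputation, define its standard error (including when a dataset has no responders), and report the same asymptotic test in the LOCF and tipping-point analyses.

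The sponsor is fully unblinded from the Week 48 primary analysis (SAP 1.5), and SAP Amendment 2 follows past interim analyses. Date the clarification relative to that unblinding, state which rule any earlier analysis used, and report the result under the other rule beside it. Naming the one-sample test in SAP 5.3.2.3 and 5.3.3.1.1 is an editorial tidy-up.

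The cost is SAP wording, a few lines of code and one extra reported p-value per arm. No participants or design changes are involved.

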5.3.2.2. Sensitivity Estimators of the Main Estimand of the Key Secondary Endpoint

Sensitivity analyses will be conducted by constructing three sensitivity estimators for the key secondary primary estimand as defined in Section [5.3.2](#). One estimator will test the assumption of homogeneous treatment effect across the 2 randomization stratification factors, and the 2 other ones will use different missing data imputation rules.

5.3.2.2.1. Sensitivity Estimator 1 For the Main Estimand (LOCF) of the Key Secondary Endpoint

For this sensitivity estimator 2, the same statistical model (Clopper-Pearson and stratum-adjusted MH test), data included and approach to control the Type I error rate will be used as for the main estimator (Section 5.3.2.1). The assumption for missing data and the rule to handle missing data have changed.

5.3.2.2.1.1. Assumptions

- Missing Data for HBsAg are Missing Completely at Random ([Barnes A. et al., 2008](#))
- The treatment effect is homogeneous across strata

5.3.2.2.1.2. Missing Data Handling Rule

For sensitivity estimator 2, participants who withdraw from the study prior to Week 72 will be considered as non-responders. After taking into account all the intercurrent events and applying the intercurrent event strategies specified in Section 5.3.2, if a subject who did not experience any ICEs has missing response status for the key secondary efficacy endpoint then the LOCF approach will be used as follows.

If the HBsAg value is missing at Week 72, the Last Observation Carried Forward (LOCF) in conjunction with the next available observation imputation approach will be used. The non-missing value closest to Week 72 will be selected among the non-missing values which are no earlier than 12 weeks prior or no later than 12 weeks after Week 72. If 2 non-missing laboratory values are equidistant, the later observation will be preferred.

For Mod-step, model averaging techniques across the statistically significant candidate models obtained from the MCP step will be used to derive the dose-response shape (Mod step).

5.3.2.2.2. Sensitivity Estimator 2 For the Main Estimand (Tipping Point) of the Key Secondary Endpoint

For this sensitivity estimator 3, the same statistical model (MCP-Mod, Clopper-Pearson and stratum-adjusted MH test), data included and approach to control the Type I error rate will be used as for the main estimator (Section 5.3.2.1). The assumption for missing data and the rule to handle missing data have changed.

5.3.2.2.2.1. Assumptions

- Missing Data for HBsAg are Missing Not at Random (MNAR)
- The treatment effect is homogeneous across strata

5.3.2.2.2.2. Missing Data Handling Rule

For sensitivity estimator 3, the tipping point approach with the exhaustive scenario's analysis will be applied.

Instead of imputing non-response for missing data, the following method will be utilized to vary the imputation of response for missing data. For participants with missing response data at Week

72, responder status will be imputed in an increasing manner by participant count for each treatment group. Specifically, for each participant with missing data at Week 72, a responder/non-responder status will be imputed starting with the scenario where all participants are non-responders up to the scenario where all participants are responders. This would include all possible scenario combinations of responder/non-responder status for all missing data, including scenarios where participants on any active Arm have worse outcomes than participants on placebo+placebo+NA. Within the exhaustive scenarios list, the ‘worst case scenario’ will be one of the cases where all participants with missing Week 72 data in the active regimen arms will be imputed to ‘non-responders’ and all participants with missing data at Week 72 in the placebo+placebo+NA arm will be imputed to “responders”. For each scenario, the same statistical model (MCP-Mod, Clopper-Pearson, and stratum-adjusted MH test), will be used as for the main estimator of comparisons vs historical control and comparisons amongst the combination regimens (Section 5.3.2.1.1) will be performed. A graphical display of the pvalue significance will summarize the results across all scenarios for this sensitivity estimator 3.

